
regulate expression of numerous genes. Interestingly, digoxin does not alter PKM2 kinase activity but suppresses PKM2 dependent transcriptional activity. This area is significant because sterile inflammation (SI) is the central pathological process in AH. Our results identify PKM2 as a key molecule in liver sterile inflammation which can be therapeutically targeted. The identification of digoxin as a PKM2 binder, which leads to critical anti-inflammatory effects, provides a novel opportunity to reduce liver inflammation in AH. We have further identified a unique molecular profile from a pilot aptamer-proteomic screen which will be expanded to the whole InTeam cohort to provide predictive markers for severe AH.

4. **Research Plan:** Summarize the study design and research procedures using non-technical language that can be readily understood by someone outside the discipline. **Be sure to distinguish between standard of care vs. research procedures when applicable, and include any flowcharts of visits specifying their individual times and lengths.** Describe the setting in which the research will take place.

Test if administering digoxin orally to healthy subjects results in a reduction in innate immune inflammatory responses in the peripheral blood.

We need to obtain peripheral blood lymphocytes from healthy subjects on different doses of digoxin to test if digoxin has an effect on the immune response of PBLs.

A) There will be three study groups.

Groups:

A: Placebo n=15

B: Digoxin 3 mcg/Kg/day n=15

C: Digoxin 0.15 mcg/Kg/day n=15

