F) Pregnancy: *The chance of a female subject to become pregnant on a 4-week study is very less, if in case this does happen they will be asked to stop the drug and withdraw from the study immediately. We do not intend to follow the pregnancy and birth outcome.*

Drug preparation: Digoxin is commercially available as a 0.05mg/ml elixir (Boehringer Ingelheim). The appropriate dosing of digoxin and control will be prepared with the help of the Yale Center for Clinical Investigation (YCCI) as detailed in the facilities and resources. Stopping criteria: Subjects will be removed from the study if any serum digoxin level is above 0.8ng/ml, or if there are any abnormalities in blood tests or ECGs. Data from these subjects will not be used in the analysis. Analysis, expected outcome and alternative approaches: It is expected that there will not be a significant difference in the neutrophil ROS and monocyte qPCR results in control group A between the four time points. It is expected that for group B and C, both neutrophil ROS and monocyte qPCR levels will be lower at time points 1, 2, 3 weeks as compared to time 0, and as compared to all time points of group A. It is not clear if in group D time points of week 1, 2, and 3 will be any different from time point 0. For the time points where significant differences are found we will perform additional luminex assay with the supernatant using the luminex five plex panel (GM-CSF, IL-1B, IL-6, IL-8, TNF- α). There will also be an analysis of the production of ROS and qPCR levels in relation to serum digoxin levels at the time that the analysis samples were obtained. The combinations of these analysis will establish that digoxin taken orally is effective in reducing inflammatory responses, and will also provide information on dose response for oral dosing as well as serum concentrations.

5. Genetic Testing N/A

A. Describe

- i. the types of future research to be conducted using the materials, specifying if immortalization of cell lines, whole exome or genome sequencing, genome wide association studies, or animal studies are planned *Write here*
- ii. the plan for the collection of material or the conditions under which material will be received *Write here*
- iii. the types of information about the donor/individual contributors that will be entered into a database *Write here*
- iv. the methods to uphold confidentiality *Write here*

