- Risks and Inconveniences of an electro-cardiogram (EKG): EKG is very safe procedure which is being performed very commonly for evaluation of cardiac status. There is no risk of performing EKG to the subjects, however, there may be slight inconvenience of cold sensations to the skin related to the application of gel at the site of EKG leads placement.

11. **Minimizing Risks:** Describe the manner in which the above-mentioned risks will be minimized.

1. Each participant will be enrolled only after signing an informed consent in the presence of a study coordinator. Participants will have adequate opportunity to review the informed consent and to ask any questions they may have about the research protocol, compensation, risks, and benefits of taking part in the study.
2. Blood draws and other biological sample collections will be performed by trained personnel. pregnancy testing for female participants of childbearing potential and a baseline screening to determine if you are eligible for this study.
3. A written detailed collection procedure is provided to minimize spilling during collection.
4. Serum digoxin concentrations, BUN, Creatinine, CBC and ECGs will be obtained weekly to monitor the adverse effect of digoxin. In case, subject is having adverse effect related to digoxin, they will be removed from study and medical care will be provided at Yale new haven hospital if needed.
5. In terms of potential drug allergies, all subjects will be asked standardized questions about previous allergic reactions to digoxin. If a participant reports a digoxin allergy, they will be excluded. We will contact (telephone, email, or text message) each participant within three days of starting the oral digoxin in order to assess tolerability.

6. There may be low risk of breach of confidentiality, however we will follow appropriate data safety plan to minimize the breach of confidentiality. In addition, unauthorized personnel will not be allowed to have access to subject's confidential information.

7. If study subjects express a desire to discontinue the protocol, for any reason, the intervention will be immediately terminated and consent to participate may be rescinded at the subject's discretion.

12. Data and Safety Monitoring Plan: Include an appropriate Data and Safety Monitoring Plan (DSMP) based on the investigator's risk assessment stated below. (Note: the HIC will make the final determination of the risk to subjects.)

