Adherence analysis will be ascertained using pill counts for each participant at the weekly visits. For safety analyses, we will record any adverse events, both serious (SAE) and not, described by the participant at each weekly visit. Each AE will include a description of the AE/SAE, relatedness to digoxin, and resolution. These will be summarized by treatment group and, if there are three or more participants in any one group with a specific AE/SAE, we will conduct a statistical test (Likelihood Ratio Chi-Square) to determine any statistically significant difference among the treatment groups using the analogous approach as above to first test for any difference in the incidence of AE/SAE among the three treatment groups followed by conducting the three pairwise comparisons, again using the Likelihood Ratio Chi-Square. Because this is a safety analysis, the critical p-value is left at 0.05 for all comparisons to avoid increasing the probability of a Type II error.

SECTION II: RESEARCH INVOLVING DRUGS, BIOLOGICS, RADIOTRACERS, PLACEBOS AND DEVICES

If this section (or one of its parts, A or B) is not applicable, check off N/A and delete the rest of the section.

A. RADIOTRACERS

N/A

1. Name of the radiotracer: *Write here*
2. Is the radiotracer FDA approved? YES NO

If NO, an FDA issued IND is required for the investigational use unless RDRC assumes oversight.

3. Check one: IND# *Write here* or RDRC oversight (RDRC approval will be required prior to use)
4. **Background Information:** Provide a description of previous human use, known risks, and data addressing dosage(s), interval(s), route(s) of administration, and any other factors that might influence risks. If this is the first time this radiotracer is being administered to humans, include relevant data on animal models.
Write here
4. **Source:** Identify the source of the radiotracer to be used. *Write here*
5. **Storage, Preparation and Use:** Describe the method of storage, preparation, stability information, method of sterilization and method of testing sterility and pyrogenicity.
Write here

B. DRUGS/BIOLOGICS

N/A

1. If an **exemption from IND filing requirements** is sought for a clinical investigation of a drug product that is lawfully marketed in the United States, review the following categories and complete the category that applies (and delete the inapplicable categories):

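### Removal rules fall mainly on the digoxin arms, yet adverse events are compared as crude incidence without regard to time observed, so a digoxin excess can be understated

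*Combined protocol and SAP*

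**What the plan says.** The trial has three arms: placebo (15 subjects), "B: Digoxin 3 mcg/Kg/day n=15" and "C: Digoxin 0.15 mcg/Kg/day n=15". Three triggers end participation:

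- **Related adverse effect** (Section I, item 11, Minimizing Risks, point 4): "In case, subject is having adverse effect related to digoxin, they will be removed from study".
- **Serum level, or abnormal blood test or ECG** (Section I, item 4, Research Plan, part F, stopping criteria): subjects are "removed from the study if any serum digoxin level is above 0.8ng/ml, or if there are any abnormalities in blood tests or ECGs". This sentence holds two triggers. It is followed by: "Data from these subjects will not be used in the analysis".

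The safety paragraph of Section I, item 13 (Statistical Considerations) records adverse events (AEs) "described by the participant at each weekly visit". The items listed for each AE are its description, relatedness and resolution; onset date is not listed. If at least three participants in one group have a given AE, the plan is to "first test for any difference in the incidence of AE/SAE among the three treatment groups" by likelihood ratio chi-square, followed by the three pairwise tests, all at 0.05. Neither item 13 nor the safety monitoring plan in item 12 mentions person-time, censoring, time to event, or AE collection after removal.

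**The concern.** A crude proportion is a fair comparison only if the arms are watched for about the same time. A subject removed at the week 1 visit can report one week of events, against three weeks for a subject who completes the visits at weeks 1, 2 and 3. If removal is more common on digoxin, placebo subjects have more opportunity to report headache, nausea and other background events, and the comparison is pulled toward no excess on digoxin. The more often digoxin itself causes removal, the stronger the pull.

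This runs against the plan's own priority. Item 13 leaves the safety threshold at 0.05 in order not to raise the Type II error, and shorter observation on digoxin raises that error.

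**Working it through.** The documents give no AE rate, removal rate or power for the safety comparison, so there is no planned figure to reproduce.

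**From the documents:** 15 subjects per arm; visits at weeks 0, 1, 2 and 3; at least three participants with the AE in one group before testing; threshold 0.05.

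**Assumed:** three weeks of observation; a constant weekly probability *p* of a first event; a share *r* of a digoxin arm removed at the week 1 visit for a reason unrelated to the AE being compared; no placebo removals; AEs before removal kept, none collected afterwards.

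**Step 1, crude incidence.**

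- Placebo: 1 − (1 − p)³. With p = 0.10 this is 1 − 0.729 = 27.1%.
- Digoxin: (1 − r)[1 − (1 − p)³] + r·p. With p = 0.10 and r = 0.20 this is 0.80 × 0.271 + 0.20 × 0.10 = 23.7%.

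For a true excess, take p = 0.15 on digoxin: 1 − 0.85³ = 38.6%, a true difference of 11.5 points from placebo.

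| Removed at week 1 | No true effect: digoxin incidence | Difference from 27.1% | True excess: digoxin incidence | Difference from 27.1% |
|---|---|---|---|---|
| 0% | 27.1% | 0.0 | 38.6% | +11.5 |
| 10% | 25.4% | −1.7 | 36.2% | +9.1 |
| 20% | 23.7% | −3.4 | 33.9% | +6.8 |
| 40% | 20.3% | −6.8 | 29.2% | +2.1 |
| 60% | 16.8% | −10.3 | 24.4% | −2.7 |

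In an arm of 15, 1.7 to 3.4 points is 0.3 to 0.5 of a participant, and 6.8 points is about one. In the true-excess case the sign reverses when r exceeds (38.6 − 27.1)/(38.6 − 15.0) = 11.5/23.6, or about 49%.

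**Step 2, a second model.** Assume a constant hazard, a 20% three-week risk on placebo, and a digoxin hazard ratio of 2. The crude risk ratio is 1.80 with no removal and 1.43 with 33% removed at week 1. Exact enumeration of 15 against 15 (pairwise test, at least three events in one arm) puts the chance of a significant excess on digoxin at 17.4% and 9.0% respectively. For an AE with no digoxin effect, the chance of a significant result favouring digoxin rises from 3.4% to 6.4%. With 33% removed, an AE looks neutral or protective only if its true hazard ratio is below 1.31; with 50% removed, below 1.54.

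**Step 3, rates per person-week.** A subject followed for three weeks contributes 1 + (1 − p) + (1 − p)² expected weeks at risk; with p = 0.10 this is 2.71. A subject removed at week 1 contributes 1. With r = 0.20, first events are 0.2368 per subject and person-weeks are 0.80 × 2.71 + 0.20 = 2.368, so the rate is 0.10, the true value. This holds for any *r* under the assumptions above.

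**Step 4, where the rate also fails.** Suppose the 20% removed have a weekly risk of 40% and the rest 10%. The observed rate is (0.20 × 0.40 + 0.80 × 0.271)/2.368 = 0.125. With full follow-up it would be (0.20 × 0.784 + 0.80 × 0.271)/(0.20 × 1.96 + 0.80 × 2.71) = 0.146. Removal linked to later risk still leaves some understatement.

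**The case against.** Five points can be made in the plan's defence.

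1. **The rules are not digoxin-only.** A reader who sees the related-effect and serum-level triggers might infer that they are. The abnormal blood test or ECG trigger covers placebo too, and the related-effect wording does not exclude a placebo subject whose event is judged related. If 40% of every arm left at week 1, and a further 20% of those remaining in a digoxin arm also left, the no-effect incidences would be 20.3% and 18.2%, a gap of 2.1 points instead of 3.4. This stands: removal falls mainly, not only, on digoxin.
2. **The AE that triggers removal is already counted.** Its first-event incidence loses nothing, so it does not follow that digoxin harm in general is understated. This stands; the bias concerns other and later AEs.
3. **The data exclusion may change the problem.** If "Data from these subjects will not be used in the analysis" covers AEs, subjects removed under the stopping criteria leave the comparison and cause no unequal time. The text does not say whether it does. That reading brings a different distortion: a true 6/15 against 3/15 becomes 3/12 against 3/15 if three digoxin cases are dropped. The point therefore has to be settled first.
4. **The documents do not say that AE collection stops at removal.** True. Care is offered to removed subjects, and resolution is recorded. But the only AE collection item 13 describes is at the weekly visit.
5. **Heavy removal is unsupported.** Section II, part B (Drugs/Biologics), item 2 says the dose was chosen to keep levels within or below the therapeutic range. On the other side, the sample size rationale in item 4 acknowledges that absorption varies between people. Neither supplies a rate.

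**Conclusion.** The point holds in a limited form. The planned AE comparison ignores time observed in a design whose removal rules can shorten observation more on digoxin. For AEs other than the triggering one, a digoxin excess can then be understated. Under the stated assumptions the distortion is about 2 to 3 points at 10 to 20% removal in week 1 and about 7 points at 40%. The direction rests on more removals on digoxin than on placebo, on pre-removal AE data being kept, and on no collection afterwards.

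A reader might infer that the plan makes digoxin look protective. The documents do not support that as an expected result: with a true weekly risk of 15% against 10%, it needs about half the arm removed at the first visit, and nothing in the documents suggests this. Low precision with 15 per arm is the larger limitation. Even with full follow-up, a hazard ratio of 2 at 20% placebo risk is detected about 17% of the time. That does not justify leaving in a directional bias that is cheap to reduce.

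**What to change.** Amend the safety paragraph of Section I, item 13:

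- State that AE data from all treated subjects, including those removed, stay in the safety analysis, and that the data exclusion under the stopping criteria does not apply to it.
- Derive weeks observed for each subject and AE term, from first dose to first event or last visit.
- For each AE term and arm, report first events per person-week with an exact Poisson rate ratio, or time to first AE censored at last contact. Show these next to the crude proportions.
- Tabulate removals by arm, week and reason.
- State the limits: the rate comparison assumes roughly constant weekly risk and removal unrelated to later AE risk; removal for a high level may be informative; precision stays low with 15 per arm.

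The documents also describe the observation period differently: last sampling at week 3 in item 4, and 28 days in item 10 (Risks). These should be reconciled, because they set the time at risk.

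The cost is analysis-plan wording and one derived variable from visit dates the trial already has. If only the visit of first report is known, time to event is accurate to the week. No extra subjects are needed and the removal rules do not change.

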Serum digoxin concentrations, BUN, Creatinine, CBC, Electrolytes (Na, K) and ECGs will be obtained weekly. pregnancy testing for female participants of childbearing potential and a baseline screening to determine if you are eligible for this study. Peripheral blood (25ml) in EDTA tubes (purple top) will be obtained at 0, 1, 2, 3 weeks after starting digoxin, with written consent and in accordance with the guidelines of Yale University ethics committee. PMN and monocytes will be isolated using PolymorphPrep (Axis-Shield) according to standard procedure, and purity will be determined by flowcytometric analysis. Spontaneous ROS of PMNs will be measured by culturing neutrophils with CM-H2DCFDA for 30 minutes, washing, followed by kinetic analysis of intracellular ROS with fluorescent plate reader. Neutrophils up-regulate ROS spontaneously in culture, and for each sample the untreated aliquot will be the control for the digoxin treated aliquot. Monocytes will be stimulated LPS (100ng/ml) for 3 hrs after which cDNA will be prepared and qPCR conducted for IL-1B, TNF- α and IL-6. cDNA and supernatant will be stored for further analysis based on initial results.

These initial numbers are based the use of similar assays in the preliminary data. We will obtain additional assistance from [name] Professor of Biostatistics at the University of Massachusetts, who will 1) review of study design, including sample size and specimen utilization; 2) develop an appropriate data management system to provide data capture and edit capabilities; 3) develop appropriate statistical analysis, quality assurance, and quality control plans; 4) conduct the statistical analysis and provide material for presentation/publication; and 5) provide resources to assure reproducible research. Please see letter of support.

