B) The data management system will be set up in the University of Massachusetts Medical School secure REDCap environment, which is used for all of the pilot studies funded by NIAAA as part of the AlcHepNet Research Network. This HIPAA-compliant, 21 CFR Part 11 compliant environment is accessible only by medical school staff and collaborating clinical sites of the AlcHepNet who are assigned an account in this environment by UMMS IT with approval by the UMMS IRB. The system will be programmed for a single entry with validation rules at the time of entry and additional checking conducted after the data have been submitted to the main data base. These edits will check for validity, consistency, and normal range values. Edit queries will be generated and resolved by clinic staff with corrections posted to the database through the REDCap system, which enforces an audit trail for all changes. The study database will be stored in REDCap within the secure environment to protect any PHI/PII data

that are collected as part of the study. We will strive to minimize collection of such data and REDCap will be programmed to segregate that data from the study data so that exports for analysis will be deidentified. Data will be exported from REDCap for import into the latest version of SAS (SAS Institute, Cary, NC) or other statistical software for all analysis.

C-E) All reports and analyses will be generated from these files. Data files (and accompanying programs) that are used for reports, presentations, or publication will be archived as required past the end of the study. REDCap will also have the audit trail capability enabled for tracing any data modifications. Data from laboratories can be uploaded directly into REDCap for storage. The REDCap system will be programmed and maintained by study staff at the U Mass Medical School AlcHepNet Data Coordinating Center while data entry will be performed by study staff at the local site.

The sample size for this pilot study was based on results from in vitro experiments, where differences in as few as 5 participants were seen to be significantly different. Given the inherent variability in the absorption of digoxin in humans, a sample size of 15 was determined to be reasonable to provide a reasonable distribution of results from repeated measures of participants at the differing digoxin dose levels.

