The principal investigator (*[name]*) will conduct a review of all adverse events upon completion of every study subject. The principal investigator will evaluate the frequency and severity of the adverse events and determine if modifications to the protocol or consent form are required.

Please note: For any study that may be considered high risk, the IRB will be more focused on the safety requirements for the study and a DSMB will likely be required.

- d. For multi-site studies for which the Yale PI serves as the lead investigator:N/A
 - i. How will adverse events and unanticipated problems involving risks to subjects or others be reported, reviewed and managed? *Write here*
 - ii. What provisions are in place for management of interim results? *Write here*
 - iii. What will the multi-site process be for protocol modifications? *Write here*

13. Statistical Considerations: Describe the statistical analyses that support the study design.

Primary analyses of the biochemical measures will be conducted using mixed effects models to account for the correlation among the biochemical measures obtained from repeated blood draws on the same participant. The models will include digoxin dose (3 mcg/kg/day, 0.15 mcg/kg/day, none/placebo), time on study (weeks 0, 1, 2, and 3), and relevant patient characteristics (i.e., age, gender). A random intercept will be included so that each participant will have their own starting point and time will be a categorical predictor to better model a potential curvilinear relationship between time on study and biochemical levels without assuming a linear slope. Because treatment group is a three-level variable, we will first conduct a Type III multi-degree of freedom test to determine if any difference exists among the three groups and, if that is significant, conduct all pairwise comparisons to determine where the difference is. Because these tests are not independent, we will apply a Bonferroni correction to the critical p-value to reduce the possibility of a Type I error by chance alone. In this case, the critical p-value will be set at $0.05/3 = 0.017$ so that any p-value less than 0.017 will be declared statistically significant.

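### The primary test of dose group averages the week-0 visit into the treatment contrast and does not adjust for it, so it targets 75% of the weeks 1–3 effect and loses power

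*Combined protocol and SAP*

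**What the plan says.** Section I, 13 (Statistical Considerations) gives the primary analysis as a mixed model. The listed terms are dose at three levels, visit as a categorical factor with week 0 among its four levels, age and gender. It adds: "A random intercept will be included so that each participant will have their own starting point". On testing it says "we will first conduct a Type III multi-degree of freedom test to determine if any difference exists among the three groups". The three pairwise comparisons follow only if that test is significant, at a critical value of 0.05/3. No dose-by-visit interaction and no week-0 covariate appear.

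Section I, 4 (Research Plan) says that the blood samples "will be obtained at 0, 1, 2, 3 weeks after starting digoxin". Its analysis paragraph expects that in the digoxin groups "both neutrophil ROS and monocyte qPCR levels will be lower at time points 1, 2, 3 weeks as compared to time 0", and also lower than in placebo group A. It says the analyses together "will establish that digoxin taken orally is effective in reducing inflammatory responses, and will also provide information on dose response for oral dosing".

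**The concern.** The question in the Research Plan concerns weeks 1–3, with time 0 and group A as references. The test in Statistical Considerations concerns the group factor in a model where week 0 is one of four outcome visits. At week 0 no drug effect can be present, so that visit dilutes the group contrast. The week-0 value is also the obvious variable for removing differences between participants, and the plan does not use it that way.

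The test gates every pairwise dose comparison. A false negative there ends the dose comparisons under the plan's own rule. If the group contrasts are read as drug effects, each is a quarter too small, which matters for a study meant to inform dose response.

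**Working it through.** **The plan's own figures.** The Bonferroni value reproduces: 0.05/3 = 0.0167, given as 0.017. The 15 per group cannot be reproduced, because no effect size, SD, correlation or power is stated.

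**Inputs from the documents.** Three groups of 15; visits at weeks 0, 1, 2 and 3; random intercept; no interaction or week-0 covariate listed; no drug effect at week 0.

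**Assumptions.** Complete data; total variance 1 after age and gender; within-person correlation (ICC) from 0 to 0.7; a constant effect of d SD at weeks 1–3 in one dose group (power is the same if both doses share it); overall test at 0.05.

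**Step 1: what the test targets.** With complete, balanced visits the group coefficient equals the difference in four-visit group means. Its expectation is (0 + d + d + d)/4 = 0.75d, whatever d or the ICC. If the effect varies by week, it is 0.75 of the mean weeks 1–3 effect.

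Two checks agree:
- A fitted mixed model on one simulated data set gave a group coefficient identical to the raw difference in four-visit means (−1.0326 for both).
- In 100 simulated trials with a true effect of 1 SD, the mean estimate was 0.786 (SE 0.030), identical with and without a dose-by-week term. The week-0-adjusted model gave 1.024 (SE 0.024).

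**Step 2: variances per participant.**
- Four-visit mean: ICC + (1 − ICC)/4.
- Weeks 1–3 mean: (1 + 2·ICC)/3.
- Weeks 1–3 mean given week 0: (1 + 2·ICC)/3 − ICC².

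At ICC 0.5 these are 0.625, 0.667 and 0.417.

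**Step 3: efficiency.** The ratio of adjusted to stated analysis is [1/adjusted variance]/[0.75²/four-visit variance]. At ICC 0.5 it is (1/0.417)/(0.5625/0.625) = 2.40/0.90 = 2.67. In general the stated test has relative efficiency 0.75 × (1 − ICC), which is below 1 at every ICC.

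**Step 4: power.** For one active group with contrast c, the noncentrality is 15 × (2/3) × c²/variance = 10c²/variance, referred to F with 2 and 42 df (2 and 41 adjusted). At d = 0.8 and ICC 0.5:
- stated: 10 × 0.6²/0.625 = 5.76, power 53%;
- adjusted: 10 × 0.8²/0.417 = 15.4, power 93%.

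| ICC | Power, d=0.5: stated / adjusted | Power, d=0.8: stated / adjusted | Power, d=1.2: stated / adjusted | Effect detectable with 80% power: stated / adjusted | Efficiency ratio (from dropping week 0 from the average alone) |
|---|---|---|---|---|---|
| 0 | 52 / 65% | 92 / 97% | >99 / >99% | 0.68 / 0.59 SD | 1.3 (1.3) |
| 0.1 | 42 / 58% | 83 / 95% | 99 / >99% | 0.77 / 0.64 SD | 1.5 (1.4) |
| 0.3 | 30 / 52% | 66 / 92% | 96 / >99% | 0.94 / 0.68 SD | 1.9 (1.6) |
| 0.5 | 23 / 55% | 53 / 93% | 88 / >99% | 1.07 / 0.66 SD | 2.7 (1.7) |
| 0.7 | 20 / 69% | 45 / 98% | 80 / >99% | 1.19 / 0.57 SD | 4.4 (1.7) |

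At d = 1.5 the stated test has 94.7% power at ICC 0.7 and more at lower ICC. The adjusted test exceeds 99% throughout.

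**Step 5: simulation, 6000 trials per setting, ICC 0.1/0.3/0.5/0.7.** With no effect, the stated test rejected in 4.7/4.7/5.0/4.9%. At d = 0.8 its mean estimate was 0.59–0.60, against 0.80 adjusted. Power was 83/66/52/45% against 94/91/92/97%.

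**Step 6: chance imbalance at week 0.** It enters the stated estimate with weight 1/4, so its SD is 0.25 × √(2/15) = 0.09 SD. That is noise, not bias, if the groups are comparable.

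**Step 7: the only effect-size hint.** For the in vitro work the Research Plan says "differences in as few as 5 participants were seen to be significantly different". Significance with 5 per group needs an observed difference of t(0.975, 8) × √(2/5) = 1.46 SD. If paired, it needs t(0.975, 4)/√5 = 1.24 SD of the differences.

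**The case against.** - **Visit-specific comparisons are intended.** The Research Plan also says "For the time points where significant differences are found we will perform additional luminex assay", and the listed model terms need not be exhaustive. It is fair to say that the two sections are not joined up. This does not repair the gating test: its sentence is tied to the three-level group factor, and with an interaction added a Type III group test still averages over week 0.
- **The random intercept handles baseline.** It models within-person correlation. It neither removes week 0 from the group contrast nor adjusts for it.
- **Placebo week 0 belongs in the comparison.** The Research Plan does compare the digoxin groups with every group A time point. But the digoxin groups' own week 0 is their reference, and the tested contrast counts it as treated time.
- **No effect estimate is prespecified.** True. The 25% underestimate bites when the group contrast is reported as the drug effect. The power loss does not depend on reporting.
- **The power figures are assumptions.** This stands. Wide gaps need a moderate effect with an ICC of about 0.3 or more. For ROS the untreated-aliquot control might lower the ICC, though even at ICC 0 the efficiency ratio is 1.3. Effects as large as the in vitro hint would leave a small to moderate loss. The table also omits a graded response: with 1 SD and 0.5 SD in the two dose groups and ICC 0.3/0.5/0.7, power is 73/60/51% as written and 95/96/99% adjusted.
- **It is a pilot, and type I error is preserved.** Both are true and limit the severity. But with 15 per group and no power calculation there is little margin to give away.

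**Conclusion.** The concern holds. As written, the primary test targets 0.75 of the mean weeks 1–3 effect. This is exact for complete visits and no effect at week 0; missed visits would shift the fraction somewhat. Efficiency is lost at every within-person correlation, and only the amount rests on an assumed effect size and ICC. The test remains valid at its nominal level if the groups are comparable at week 0, so this is a weakness of sensitivity and estimation, not of false-positive control. It should be fixed before the data are analysed.

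**What to change.** In Section I, 13, make weeks 1–3 the outcome visits and enter the participant's week-0 value as a covariate. Include group, week, group-by-week, age, gender and the random intercept. Define the primary two-degree-of-freedom test as equality of the group means averaged over weeks 1–3, and make the three pairwise comparisons on that same average. A longitudinal model with a constrained common baseline is an alternative. The covariate form is safer here because the documents describe no randomisation and the constrained model assumes equal baseline means. As a secondary point, take the week-specific group contrasts that trigger the Luminex assays from the same model.

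The cost is a change of wording in the analysis plan and one degree of freedom. The week-0 samples are already scheduled.
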